5.5 EVALUATION OF DEVICE DEFICIENCIES

Device deficiencies will be tabulated and listed in a manner similar to the methods described for adverse events. Any device deficiency leading to an adverse event or study termination will be listed separately.

6 ANALYSIS OF SECONDARY EFFECTIVENESS ENDPOINTS

The secondary effectiveness objective is to evaluate additional glycemic measures of effectiveness of the Omnipod Horizon[™] Automated Glucose Control System. The secondary effectiveness objective will be evaluated based on the secondary effectiveness endpoints listed in Section 3.3 above.

6.1 ANALYSIS OF PERCENTAGE OF TIME IN RANGE

The analysis of secondary endpoints that summarize the percentage of time in range (TIR) will follow the analysis set forth for the primary effectiveness endpoint of TIR 70-180 mg/dL, with the range value updated as appropriate.

6.2 ANALYSIS OF PERCENTAGE OF TIME IN HYBRID CLOSED-LOOP

The percentage of time in hybrid closed-loop will be calculated as:

 $100 \times \frac{\text{sum of gaps between consecutive CGM readings}}{\text{difference between the earliest and the latest CGM readings}} = \% \text{ time in HCL}$

A gap is calculated as the difference in time (either minutes or seconds) between two consecutive CGM records as captured by the Horizon[™] System. The gaps are then summed to obtain total time in HCL. As records are generally taken in about every 5 minutes, and to ensure that only confirmed HCL records are included, gaps greater than 7 minutes will be excluded from analysis. For the denominator, the chronologically earliest and latest CGM records during HCL as captured by the Horizon[™] System will be used.

As opposed to the time in range endpoints, records with no glucose value in the Horizon[™] System device output (such as due to an error or device deficiency during which the device does not record glucose readings) will be included in analysis. CGM records reported prior to the start of HCL or after the subject's discontinuation from HCL will be

Statistical Analysis Plan

excluded from analysis. This endpoint will also be reported separately for the manual and automated modes.

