2.1.1. Omnipod Horizon™ Controller (App and Algorithm)

The Omnipod Horizon™ Controller is composed of two parts: the Horizon application (“app”) and the model predictive control (MPC) algorithm on the Pod. The MPC algorithm provides insulin micro-boluses once every 5 minutes based upon the predicted glucose over a 60-minute prediction horizon. Optimal post-prandial control will require the user to give meal boluses in the same manner as current pump therapy, but normal operation of the MPC algorithm will compensate for missed meal boluses and mitigate prolonged hyperglycemia. The MPC algorithm uses a control-to-target strategy that attempts to achieve and maintain a set target glucose value, thereby reducing the duration of prolonged hyperglycemia and hypoglycemia. The MPC algorithm resides on the Pod (Pump) component of the Omnipod Horizon™ System (similar to the DASH ACE pump cleared in K191679), as described further below).

The Omnipod Horizon™ app will be the primary user interface and will be used to start and stop a Pod, program basal and bolus calculator settings for Manual Mode as well as program settings specific for Automated Mode (hybrid closed-loop).

Manual Mode

In Manual Mode, the Horizon™ System will function equivalently to the Omnipod® DASH System, which was first cleared under K180045, most recently under K191679. This includes delivering insulin at programmed basal rates and bolus amounts with the option to set temporary basal profiles. The Omnipod Horizon™ Controller will also have the ability to function as a sensor augmented pump in Manual Mode, using sensor glucose data provided by the iCGM to populate the bolus calculator.

Automated Mode

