3.3 SECONDARY OBJECTIVE AND ENDPOINTS

The secondary objective is to evaluate additional glycemic measures of effectiveness of the Omnipod Horizon[™] Automated Glucose Control System. The secondary objective will be evaluated based on the following per subject endpoints *with* prespecified hypotheses:

- Glucose metrics from system CGM during the hybrid closed-loop phase for Phase 2 will be compared to Phase 1 overall:
 - Percentage of time in range > 180 mg/dL
 - Percentage of time in range < 70 mg/dL

Additional per subject endpoints *without* prespecified hypotheses used to evaluate the secondary objective include:

- A1C:
 - A1C at the end of Phase 2 (Visit 13), 6 months (Visit 16) and the end of Phase 3 (Visit 19)
 - Change from baseline in A1C at the end of Phase 2 (Visit 13), 6 months (Visit 16) and the end of Phase 3 (Visit 19)
 - Proportion of subjects demonstrating an improvement from baseline in A1C at the end of Phase 2 (Visit 13), 6 months (Visit 16) and the end of Phase 3 (Visit 19)
- Glucose metrics from system CGM during the hybrid closed-loop phase for Phase 2 and Phase 3 will be compared to Phase 1 during the day, overnight, and overall:
 - Mean glucose
 - Percentage of time in range 70-180 mg/dL
 - Percentage of time in range 70-140 mg/dL
 - Percentage of time in range > 180 mg/dL
 - Percentage of time in range ≥ 250 mg/dL
 - Percentage of time in range \geq 300 mg/dL
 - Percentage of time in range < 70 mg/dL
 - Percentage of time in range < 54 mg/dL
 - Standard deviation
 - Coefficient of variation
- Percentage of time in hybrid closed-loop as proportion of overall device usage time during Phase 2 and Phase 3
- Glucose management indicator (GMI) based on overall mean glucose during Phase 2 and Phase 3 will be compared to Phase 1
- Insulin requirements during Phase 2 and Phase 3 will be compared to Phase 1:
 - Total daily insulin (TDI) (units, units/kg)
 - Total daily basal insulin (units, units/kg)
 - Total daily bolus insulin (units, units/kg)
- Change from baseline in BMI (kg/m²) at end of Phase 2 and Phase 3

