7.1.3 PP (Per Protocol) Analysis Set

The Per-Protocol (PP) analysis set is a subset of the mITT analysis set. Subjects will be included in the PP analysis set if they have a minimum of 80% system use during Phase 2 inclusive of manual and hybrid closed-loop (automated) modes over a minimum duration of 10 weeks and have completed the study without major protocol deviations. The PP analysis set will be used as supportive analysis for the endpoints. The following will be considered major protocol deviations:

- Major inclusion/exclusion criteria deviation
- Significant protocol non-compliance that may confound the study objective data (e.g., use of prohibited medications)

The list of subjects excluded from the PP analysis set will be determined prior to analysis of Phase 2 endpoints. If the PP analysis set does not differ from the mITT analysis set, separate analyses will not be presented.

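### The SAP 6.2 formula for percentage of time in hybrid closed-loop has no mode condition, so the figure reported under that name pools Manual and Automated Mode

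*SAP*

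**What the plan says.** SAP 3.3 lists, among the secondary endpoints without hypotheses, "Percentage of time in hybrid closed-loop as proportion of overall device usage time during Phase 2 and Phase 3". Protocol 6.3.1 gives the same definition. Neither document defines device usage time.

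SAP 6.2 gives the calculation.

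- **Numerator.** A gap is the time between two consecutive CGM records captured by the system. Gaps longer than 7 minutes are left out, with the stated aim "to ensure that only confirmed HCL records are included". Then: "The gaps are then summed to obtain total time in HCL".
- **Denominator.** "For the denominator, the chronologically earliest and latest CGM records during HCL" are used, so it is elapsed time.
- **Other record rules.** Records without a glucose value are kept. The section excludes "CGM records reported prior to the start of HCL or after the subject's discontinuation from HCL".
- **By mode.** "This endpoint will also be reported separately for the manual and automated modes".

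On terms, SAP 2.3 uses HCL as the abbreviation for a study phase. SAP 7.1.3 uses hybrid closed-loop for a mode, in requiring system use "inclusive of manual and hybrid closed-loop (automated) modes over a minimum duration of 10 weeks". Protocol 2.1.1 likewise gives hybrid closed-loop in brackets as the meaning of Automated Mode, as opposed to Manual Mode.

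**The concern.** The endpoint as defined is a share of device use. Such a share tells the reader something only if hybrid closed-loop means the mode in which the algorithm controls delivery. The formula instead counts every short gap between CGM records in the phase, whatever the mode. Moving CGM-connected time from Automated to Manual Mode leaves the result unchanged.

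At stake is the description of exposure. A reader of the glycemic results will want to know how much of the time delivery was automated, and the percentage carrying the endpoint's name does not answer that by itself. A second, smaller matter is that SAP 6.2 divides by elapsed time while SAP 3.3 speaks of device usage time.

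**Working it through.** The documents give no expected value for this endpoint, so there is no figure of the plan's own to reproduce. The check first reads the rule as written, then shows its effect on assumed mode shares.

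**1. Are Manual Mode records in the sum?** Protocol 2.1.1 says the controller can act as a sensor-augmented pump in Manual Mode, using CGM data. Protocol 14.2.1 says all CGM readings of the hybrid closed-loop phase are stored. SAP 6.2 filters only on gap length and on the start and end of HCL. So Manual Mode records enter the sum.

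**2. Is there a hidden mode filter?** The phrase "to ensure that only confirmed HCL records are included" could suggest one, but its only mechanism is the 7-minute rule. Records arrive about every 5 minutes, so that rule detects missing records and cannot detect mode. The planned Manual Mode version of the endpoint can exist only if Manual Mode records are in the data, and the word *also* makes the split additional to the main figure.

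**3. Algebra.** Let *r* be the share of elapsed time covered by records and *m* the share in CGM-connected Manual Mode.

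- Printed by SAP 6.2: *r*
- Automated share of elapsed time: *r* − *m*
- Automated share of usage time, taking usage time as time with records: (*r* − *m*)/*r*

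**4. Numbers.** The documents give no mode shares, so these are assumptions: *r* = 0.95, with the unrecorded 5% taken as time off the device, and *m* = 0.05, 0.15 or 0.25. Protocol section 9 asks families to manage diabetes in Automated Mode, so 25% is a stress case.

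| Manual, % of elapsed | Printed | Automated / elapsed | Printed minus this | Automated / usage | Printed minus this |
|---|---|---|---|---|---|
| 5 | 95% | 90% | 5 points | 90/95 = 94.7% | 0.3 points |
| 15 | 95% | 80% | 15 points | 80/95 = 84.2% | 10.8 points |
| 25 | 95% | 70% | 25 points | 70/95 = 73.7% | 21.3 points |

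**5. Direction.** On usage time the printed figure equals the Automated share when *r* = (*r* − *m*)/*r*, that is *m* = *r*(1 − *r*) = 0.95 × 0.05 = 4.75% of elapsed time. Below that Manual share the printed figure is too low; above it, too high. The two departures from the definition, in numerator and in denominator, partly cancel.

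**6. Check on simulated records.** SAP 6.2 was applied literally to 94 days of 5-minute records in 6-hour blocks. Automated/Manual/no-record splits of 70/20/10 and 50/40/10 both print 89.8%. Automated time is 69.8% and 49.9% of elapsed time, or 77.8% and 55.6% of usage time. A child with complete records spent wholly in Manual Mode scores 100%.

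**The case against.** The strongest reply is that SAP 6.2 largely takes care of this itself. The SAP often uses HCL for the phase. On that usage the section gives a phase total and then splits it by mode, so an Automated figure will be reported. This stands as a limit on the harm, and a reader who inferred that the Automated share will never be reported would be wrong. It does not cure the label. The pooled figure still carries the endpoint's name, and a phase total offered as a share of device use is close to a measure of record completeness. The split also lacks a stated denominator. The whole span carries over most naturally, but the text does not say so.

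A second reply concerns the denominator. A reader might infer that SAP 6.2 contradicts SAP 3.3. The documents do not go that far: device usage time is undefined, and SAP 6.2 may be the place where it is given a working meaning. The two sections need reconciling, and the usage-time column above rests on the assumption that usage means time with records.

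A third is that the formula need not flatter the system. That is right: on usage time the sign reverses at low Manual shares, which are plausible given the instruction to families.

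**Conclusion.** The point holds as a defect of definition and labelling. Followed literally, SAP 6.2 reports continuity of CGM records under a name that SAP 7.1.3 and Protocol 2.1.1 reserve for Automated Mode. Under the assumed shares the discrepancy is 5 to 25 points against Automated time on the SAP's own elapsed-time denominator, and 0.3 to 21.3 points against Automated time on usage time. These sizes depend wholly on assumed mode shares and, for the second range, on treating unrecorded time as off-device.

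The tempting stronger reading is that this undermines the study's conclusions. It does not. The endpoint is secondary, has no prespecified hypothesis, and falls under the statement in SAP 6.6 that these results will not support clinical claims. Error rates, sample size and the success criterion in SAP 2.4 are untouched.

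**What to change.** In SAP 6.2:

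1. Restrict the numerator of the named endpoint to records in Automated Mode.
2. State one common denominator for the Automated and Manual shares, consistent with SAP 3.3, and define device usage time there.
3. Keep the pooled figure but give it another name, such as *CGM record use*. A name like *system use* would invite confusion with the per-protocol criterion in SAP 7.1.3, for which no formula is given.

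The cost is a few lines of SAP text and one changed derivation. No new data are needed, because the by-mode reporting already planned in SAP 6.2 requires the mode to be known. The downside is that the percentage under the endpoint's name may be lower than the pooled figure or, depending on the denominator chosen, slightly higher.

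### The 7-minute gap rule in SAP 6.2 deducts 5 minutes too much for every run of absent records, so percentage of time in hybrid closed-loop is biased low

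*SAP*

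**What the plan says.** SAP 6.2 builds the usage figure from time differences, not from a count of records. "A gap is calculated as the difference in time (either minutes or seconds) between two consecutive CGM records", and "The gaps are then summed to obtain total time in HCL". Long gaps are then removed: "gaps greater than 7 minutes will be excluded from analysis". The section justifies this by the usual spacing of about 5 minutes and by the aim of counting confirmed records only. The denominator is the elapsed time between two records: "For the denominator, the chronologically earliest and latest CGM records during HCL" are used, with no reduction for the gaps that were removed.

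SAP 6.2 also keeps records that carry no glucose value, unlike the time-in-range calculation in SAP 7.4. The figure is to be reported separately for manual and automated modes as well.

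The endpoint is listed in SAP 3.3 among the secondary endpoints without a prespecified hypothesis. Separately, SAP 7.1.3 sets a usage threshold for the per-protocol (PP) set: "Subjects will be included in the PP analysis set if they have a minimum of 80% system use during Phase 2". That section gives no formula for system use and does not refer to 6.2.

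**The concern.** The stated purpose of the rule is "to ensure that only confirmed HCL records are included". The record that opens a long gap is itself a confirmed record, yet it receives no time. When one record is absent, two 5-minute gaps merge into one 10-minute gap, and all 10 minutes are lost from the numerator. Time is therefore taken from a record that is present as well as from the one that is not.

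The error always lowers the figure. It grows with the number of separate interruptions, not with the total time lost, so two children with the same share of records present can score differently because one has scattered losses and the other a single outage. At stake are the accuracy of a reported secondary endpoint and, only if the same formula is applied there, membership of the PP set.

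**Working it through.** **Inputs.** Record spacing about 5 minutes, exclusion threshold over 7 minutes, numerator the sum of retained gaps, denominator latest minus earliest record (all SAP 6.2). The documents give no loss rate and no length of outages, so those below are assumptions. They also give no numerical result for this endpoint, so there is no plan figure to reproduce.

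**Could the long gap leave the denominator too?** No. The denominator is defined by the first and last records. If long gaps were removed from it as well, numerator and denominator would be the same sum and every child would score 100%.

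**One run of k absent interior records, exact 5-minute grid.**
- Gap created: 5(k+1) minutes. This exceeds 7 for every k ≥ 1, so it is dropped whole.
- Time belonging to the absent records: 5k minutes.
- Ratio of deduction to loss: (k+1)/k, which is 2 at k = 1 and falls towards 1.
- Excess: 5(k+1) − 5k = 5 minutes per run, whatever k is. Since k ≥ 1, this is at most the loss itself.

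Over a 24-hour span (1440 minutes):

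| k | Deducted (min) | Lost records (min) | Ratio | SAP 6.2 result | Crediting 5 min per long gap |
|---|---|---|---|---|---|
| 1 | 10 | 5 | 2.00 | 1430/1440 = 99.31% | 1435/1440 = 99.65% |
| 2 | 15 | 10 | 1.50 | 1425/1440 = 98.96% | 1430/1440 = 99.31% |
| 3 | 20 | 15 | 1.33 | 1420/1440 = 98.61% | 1425/1440 = 98.96% |
| 12 | 65 | 60 | 1.08 | 1375/1440 = 95.49% | 1380/1440 = 95.83% |
| 24 | 125 | 120 | 1.04 | 1315/1440 = 91.32% | 1320/1440 = 91.67% |

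Records absent at the very start or end of the span cost nothing, because the denominator shrinks with them.

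**Many losses over Phase 2, independent at rate p (assumed).** A 5-minute gap survives only if both of its records are present, so the expected result is about (1−p)², against 1−p of records present:
- p = 1%: 0.99² = 98.0% against 99%
- p = 2%: 0.98² = 96.0% against 98%
- p = 5%: 0.95² = 90.25% against 95%
- p = 10%: 0.90² = 81% against 90%

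A simulation of 91 days of 5-minute slots agrees: 90.28% at 5% loss and 81.36% at 10%.

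**Losses in runs averaging L records (assumed).** The excess is about p/L:
- p = 5%: 2.5 points at L = 2, 1.67 at L = 3, 0.42 at L = 12
- p = 10%: 5.0 points at L = 2, 3.33 at L = 3, 0.83 at L = 12

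**Where the rule would reach 80%.** Under independent loss, (1−p)² = 0.80 gives 1−p = √0.80 = 89.4% of records present.

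**The case against.** The strongest defence is that the rule is deliberately conservative: an interval counts only when a record confirms it at both ends. On that reading, 10 minutes is the intended deduction, and crediting time after the last record before an outage counts time that nothing closes. This is a coherent convention. However, the SAP speaks of confirmed records, not of intervals confirmed at both ends, so it does not state it.

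Three limits on the point stand in full.
- The trigger is narrow. A record present without a glucose value opens no gap; only a record wholly absent from the output does. The documents do not say how often that happens, or whether signal loss produces absent or blank records.
- The larger figures need losses that are both frequent and scattered.
- The endpoint carries no hypothesis. SAP 6.6 says these results will not support clinical claims, the modified intention-to-treat set is primary, and PP is supportive.

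A reader might infer that usage is understated by up to twice the loss. The arithmetic does not support that: the total deduction can reach twice the loss, but half of that deduction is the loss itself.

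A reader might also infer that children with adequate use will be excluded from the PP set. SAP 7.1.3 does not say that 6.2 defines its 80%. Elsewhere (protocol 7.1 and 8.2) an 80% CGM-use criterion for Phase 1 is expressed in days of 14, so 6.2 cannot simply be assumed to apply.

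**Conclusion.** The point holds as a downward bias in a descriptive secondary endpoint. SAP 6.2 as written takes 5 minutes too much for each run of absent interior records, judged against its own aim of counting confirmed records. The size depends on an unknown loss pattern: nearly 5 points at 5% independent loss, but under half a point if the same 5% comes in runs of 12. The factor of 2 belongs to isolated single losses on a regular 5-minute grid. With irregular spacing, a gap can exceed 7 minutes with no record lost, so the factor is not a strict bound there.

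No primary endpoint and no hypothesis-tested secondary endpoint is affected. PP membership is affected only if 6.2 is the formula behind the 80% threshold, which is undetermined. This is a minor correction, worth making because it is nearly free.

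**What to change.** In SAP 6.2, keep the 7-minute threshold and the denominator. Credit gaps of 7 minutes or less in full, and credit each longer gap with one nominal 5-minute interval for the confirmed record that opens it. A run of k absent records then deducts 5k minutes, and the excess disappears on a regular grid.

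Do not instead cap every gap at 5 minutes. Records come only approximately every 5 minutes, and complete data alternating at 4 and 6 minutes would be credited 4 + 5 = 9 of every 10 minutes, or 90%. The present rule correctly returns 100% there, and the 7-minute tolerance is what absorbs that variation.

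In SAP 7.1.3, state whether the 6.2 figure defines the 80% system use and, if not, give the formula that does. This should be settled before the list of PP exclusions is drawn up.

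Cost: two sentences, one line of code and no new data. Reported usage rises slightly, and the sponsor accepts up to 5 minutes of credited time per outage with no closing record.

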6.3 ANALYSIS OF GLUCOSE MEASURES

Mean glucose, glucose measurement indicator (GMI), standard deviation (SD) of glucose and coefficient of variation (CV) of glucose will be evaluated per subject based on CGM output. The GMI and CV are calculated as follows:

 $GMI(\%) = 3.31 + 0.02392 \times (mean glucose in mg/dL)$

 $CV(\%) = \frac{SD \ of \ glucose}{mean \ glucose}$

6.4 ANALYSIS OF INSULIN REQUIREMENTS

Insulin requirements (TDI, total daily basal insulin and total daily bolus insulin) during the hybrid closed-loop phase will be compared to the standard therapy phase. The insulin requirements will be collected at Visit 2 (start of ST phase) and compared to the data collected by the Horizon[™] System during HCL:

- Total daily insulin: sum of basal and bolus insulin reported over the course of HCL, adjusted for 24-hour period
- Total daily basal insulin: sum of basal insulin reported over the course of HCL, adjusted for 24-hour period
- Total daily bolus insulin: sum of bolus insulin reported over the course of HCL, adjusted for 24-hour period. This will include only bolus insulin administered and recorded by the Horizon[™] System.

Data will be summarized both in insulin units and units/kg to provide a weight-adjusted comparison.

6.5 ANALYSIS OF SECONDARY EFFECTIVENESS ENDPOINTS WITH PRESPECIFIED HYPOTHESES

There are two secondary effectiveness endpoints with prespecified hypotheses. The modified Intention to Treat (mITT) analysis set will be the primary analysis set used to analyze the secondary effectiveness endpoints. The results based on the Per Protocol (PP) analysis set will be considered supportive.

Percentage of Time in Range >180 mg/dL

The percentage of TIR >180 mg/dL during Phase 2 of hybrid closed-loop phase will be compared to standard therapy (Phase 1) by calculating the change between the time in range percentages between Phase 2 and Phase 1 for each subject. The change is

Statistical Analysis Plan

calculated as the percentage of time in range during Phase 2 minus the percentage of time in range during Phase 1. The null hypothesis associated with this endpoint states that the mean change in percentage of time in range >180 mg/dL is greater than or equal to zero. Rejection of the null hypothesis indicates that the observed data support the alternative hypothesis that the mean change in percentage of time in range >180 mg/dL is less than zero. The hypotheses associated with the second primary effectiveness endpoint are defined as:

H0: µ ≥ 0 H1: µ < 0

where μ is the mean of the per subject differences in percentage of time in range >180 mg/dL during Phase 2 of hybrid closed-loop compared to the standard therapy phase (Phase 1).

Percentage of Time in Range <70 mg/dL

The percentage of TIR <70 mg/dL during Phase 2 of hybrid closed-loop phase will be compared to standard therapy (Phase 1) by calculating the change between the time in range percentages between Phase 2 and Phase 1 for each subject. The change is calculated as the percentage of time in range during Phase 2 minus the percentage of time in range during Phase 1. The null hypothesis associated with this endpoint states that the mean change in percentage of time in range <70 mg/dL is greater than or equal to zero. Rejection of the null hypothesis indicates that the observed data support the alternative hypothesis that the mean change in percentage of time in range of time in range <70 mg/dL is less than zero. The hypotheses associated with the second primary effectiveness endpoint are defined as:

where μ is the mean of the per subject differences in percentage of time in range <70 mg/dL during Phase 2 of hybrid closed-loop compared to the standard therapy phase (Phase 1).

If at least one of the primary effectiveness endpoints are found to be significant, the testing for secondary endpoints can commence. To maintain the family-wise error rate at one-sided 2.5% the testing will commence hierarchically, and Holm's correction will be applied as follows:

• A paired t-test will be applied to each of the secondary endpoints and the unadjusted p-values will be ordered from the smallest to largest.

- The hypothesis associated with the smallest unadjusted p-value will be tested for significance at a one-sided significance level of 2.5% / 2 = 1.25%.
- If the null hypothesis is rejected for the first hypothesis, the testing of the second hypothesis (with the higher unadjusted p-value) will commence, and the hypothesis will be tested for significance at a one-sided significance level of 2.5%. If the first null hypothesis is not rejected, the testing will stop.

